11.5 Safety Analyses

11.5.1 Extent of Exposure

The extent of exposure to study product on the face in each treatment group will be summarized as the total number of applications.

11.5.2 Local Cutaneous Safety Evaluation

Non-lesional erythema, peeling, dryness, burning, stinging, and itching scores will be summarized by treatment group and visit including sample size, frequency count and percentage for each visit. A similar summary will be provided excluding subjects with signs or symptoms present at Baseline.

11.5.3 Adverse Events

All AEs occurring during the study will be recorded and classified on the basis of Medical Dictionary for Regulatory Activities (MedDRA) terminology. Treatment-emergent adverse events (TEAEs) are AEs with an onset on or after the date of the first study product administration. For the safety population, all reported TEAEs will be summarized by treatment group, the number and percent of subjects reporting events, system organ class (SOC), preferred term (PT), severity, relationship to study product, and seriousness. When summarizing TEAEs

by causality and severity, each subject will be counted only once within a system organ class or a preferred term by using the event with the greatest relationship and highest severity within each classification.

Additionally, treatment-related TEAEs will be summarized for each treatment group by SOC and PT, and further by severity. A TEAE will be considered treatment-related if it is reported as possibly, probably, or definitely related to study treatment.

SAEs will be listed by subject. In addition, a list of subjects who prematurely discontinued from the study due to an AE will be provided.

All information pertaining to AEs noted during the study will be listed by subject, detailing verbatim term given by the investigator, preferred term, system organ class, onset date, resolution date, maximum severity, seriousness, action taken regarding study product, corrective treatment, outcome, and drug relatedness. The event onset will also be shown relative (in number of days) to date of first administration.

AEs related to study procedures done before study product administration will be provided in a data listing.

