7.3 Demographic and Baseline Characteristics

Demographic variables include age (computed from date of birth and Day 1 date), race, ethnicity, and sex. Baseline characteristics include IGA and lesion counts of the face.

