7.6 Safety Assessments

Safety assessments include visual inspection of the skin (erythema, scaling [peeling]) prior to dose application, assessment of application site reactions (dryness, non-lesional erythema, peeling, stinging, burning, and itching) after dose application, clinical safety laboratory evaluations (chemistry, hematology, and urinalysis), and physical examinations including vital signs (blood pressure and pulse rate). A 12-lead ECG will be performed at the Screening Visit, Baseline visit (Day 1) and Day 21. For females of childbearing potential serum pregnancy tests will be conducted at the Screening Visit and urine pregnancy tests will be conducted at Day 1, Day 7, Day 14 and Day 21. Adverse events will be collected by spontaneous reports from subjects, by directed questioning of subjects, and by observation (see Section 8 for details about AEs). Adverse events, whether believed by the investigator to be related or unrelated to treatment, will be recorded on the CRF.

Before each dose application, the investigator or designated trained site staff will visually inspect the skin and grade erythema and scaling using the scales shown in [Table 6](#) and [Table 7](#), respectively.

After each dose application, the investigator or designated trained site staff will assess application site reactions by examining treated areas for clinically significant non-lesional erythema, peeling, and dryness that will be graded as shown below ([Table 6](#), [Table 7](#), [Table 8](#)) and recorded on the CRF. Assessments will be recorded separately for the face and (if applicable) neck, chest and/or back (including shoulders). The investigator or designated trained site staff will also ask the subject if any stinging ([Table 9](#)), burning ([Table 10](#)), or itching ([Table 11](#)) has occurred on the face (neck, chest and/or back (including shoulders), if applicable since the previous drug application. Day 1 assessments are made prior to first application. An AE should be recorded if the severity is worse than at Day 1. In addition, overall cutaneous tolerance should be graded at Day 21, or the last visit if earlier, using the grading shown in [Table 12](#). The local cutaneous tolerance signs and symptoms will be assessed separately for the

face and neck, chest and/or back (including shoulders) using the same scales below and should be performed within 1 hour of dose application.

Table 6: Scoring of Non-Lesional Erythema

Severity	Score	Description

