8 ADVERSE EVENTS

Adverse events will be collected by spontaneous reports from subjects, either verbal or recorded in the subject diary, by directed questioning of subjects, and by observation.

The most common frequently reported adverse reactions during clinical trials with tazarotene cream 0.1% for the treatment of acne were desquamation, dry skin, erythema, and burning sensation, occurring in 10% to 30% of subjects. Adverse reactions occurring in 1% to 5% of treated subjects included pruritus, irritation, face pain, and stinging.

The investigator is to pay special attention at each visit to any signs of clinically significant dryness, non-lesional erythema, and peeling and report as an AE subsequent to the Baseline Visit if worse than at Baseline.

An AE is any untoward medical occurrence in a subject participating in a clinical trial. The event does not necessarily have to have a causal relationship with the study product. An AE can therefore be any sign, symptom, or disease, or any worsening of an existing sign, symptom, or disease, whether or not considered related to the study product or trial procedures, including injuries.

Any medical condition that is present at the time of Screening or Baseline should be considered as medical history and reported on the medical history CRF and should not be reported as an AE except for AEs observed at the Baseline Visit due to study procedures performed at the Screening visit, which should be reported. Anticipated day-to-day fluctuations of pre-existing conditions should not be reported as AEs. Unexpected worsening of pre-existing conditions should be reported as AEs. The disease or condition being studied or expected progression, signs, or symptoms of the disease or condition being studied such as worsening of acne should not be reported as an AE unless it is more severe than expected, results in discontinuation from the study or requires alternative therapy.

All serious adverse events (SAEs), all study product-related events, and all AEs leading to study product discontinuation must be followed until the clinical outcome is determined or until all attempts to determine resolution of the event are exhausted (not recovered is not an acceptable outcome for acute conditions). For other AEs, the status at the last visit can be entered into the CRF.

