11 STATISTICAL CONSIDERATIONS

All statistical processing will be performed using SAS[®] unless otherwise stated. Two-sided hypothesis testing will be conducted for all inferential analyses using a significance level of 0.05. Efficacy analyses performed using the intent-to-treat (ITT) population will be considered primary. Efficacy analyses performed using the per-protocol (PP) population will be considered supportive. Safety analyses will be performed on the safety population (all subjects who receive study product and provide any post-baseline safety information). Study populations are defined in Section 11.2.

A Statistical Analysis Plan, describing all statistical analyses and outlier testing, will be provided as a separate document prior to database lock and unblinding of the study treatments.

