11.2 Analysis Data Sets

11.2.1 Safety Population

All subjects who receive at least one confirmed dose of study product and provide any post-baseline safety information will be included in the safety population. No imputation will be made for missing safety data.

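### The protocol's stated TEAE and local tolerance tables pool adults and children within each arm, although age is the randomisation stratum; splitting them by stratum is a cheap, minor improvement

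*Combined protocol and SAP*

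**What the plan says.** Section 11.5.3 (Adverse Events): "For the safety population, all reported TEAEs will be summarized by treatment group". Treatment-related TEAEs are tabulated for each arm in the same way, by system organ class, preferred term and severity. Section 11.5.2 (Local Cutaneous Safety Evaluation) says that the tolerance "scores will be summarized by treatment group and visit including sample size, frequency count and percentage for each visit"; its only further cut leaves out subjects with signs or symptoms at baseline.

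The safety population in Section 11.2.1 is "All subjects who receive at least one confirmed dose of study product and provide any post-baseline safety information", so Part A (adults) and Part B (children) are analysed together. No safety subsection of Section 11 mentions age stratum, study part or the 9-11 group.

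Section 4 stratifies randomisation by age, with 12 adults per arm and, in children, about 26 on Test and 12 on Reference. Part B is to include at least 6 subjects aged 9-11. Under Section 5.2 the Reference arm starts at age 12, so those subjects can only be on Test, and they are exempt from inclusion criteria 6 to 8. Section 6.2 gives them about 4 g per application instead of 5 g.

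Section 11 leaves the detail to another document: "A Statistical Analysis Plan, describing all statistical analyses and outlier testing, will be provided as a separate document". That SAP is not in the text available.

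**The concern.** The trial randomises within age strata, and Section 11.1 justifies the sample size by the wish to represent both children and adults. The stated safety tables then drop that division. Two things follow.

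First, half of the Reference arm and more than half of the Test arm are children, yet no stated table shows their rate of TEAEs or their tolerance scores. The youngest children, who have a different dose and looser entry criteria, are merged with adults.

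Second, the child share differs between arms, so if event rates differ by age, the pooled Test-Reference contrast carries some of that difference even when treatment has no effect in either stratum.

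At stake is how useful the safety report is for children using a face-wash retinoid. No formal test is affected.

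**Working it through.** **Inputs.** Adults: 12 Test, 12 Reference. Children: about 26 Test and 12 Reference at the Part B maximum of 38 (Section 4). Check: 12 + 12 + 26 + 12 = 62, the planned total.

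Two smaller cases for Test children:
- 20, from the Part B target of 32 less 12 Reference. This assumes that Reference stays at 12; the documents do not give this split.
- 16, the minimum number of evaluable Test children in Section 4, again with 12 Reference.

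**Age mix in the arm contrast.** Let d be the adult-child difference in an event rate, with no treatment effect in either stratum. The pooled arms then differ by d × (Test child share − Reference child share). The Reference child share is 12/24 = 0.500.

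The documents give no age-specific rate. As assumptions, take a child rate of 10% with adult rates of 20% (d = 10 points) and 30% (d = 20 points). Section 8 reports "desquamation, dry skin, erythema, and burning sensation, occurring in 10% to 30% of subjects", but that range runs across reactions, not ages, so it is no evidence for any particular d. SE = √[pT(1−pT)/nT + pR(1−pR)/nR], with nR = 24.

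| Test children | Test child share | Age mix | d = 10: Test vs Reference; gap; SE | d = 20: Test vs Reference; gap; SE |
|---|---|---|---|---|
| 16 | 16/28 = 0.571 | 0.071d | 14.3% vs 15.0%; 0.7; 9.8 | 18.6% vs 20.0%; 1.4; 11.0 |
| 20 | 20/32 = 0.625 | 0.125d | 13.75% vs 15.0%; 1.25; 9.5 | 17.5% vs 20.0%; 2.5; 10.6 |
| 26 | 26/38 = 0.684 | 0.184d | 13.2% vs 15.0%; 1.8; 9.1 | 16.3% vs 20.0%; 3.7; 10.1 |

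The gap is 0.07, 0.13 and 0.20 of an SE at d = 10, and 0.13, 0.24 and 0.36 of an SE at d = 20. If children had the higher rate, the sign would reverse.

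**Distance of the pooled rate from the paediatric rate.** This is d × adult share. Test: 12/28 = 42.9%, 12/32 = 37.5% or 12/38 = 31.6% of d. Reference: 12/24 = 50% of d. At d = 10 that is 4.3, 3.8 or 3.2 points in Test and 5.0 in Reference. The SE of a 10% paediatric rate, √(0.1 × 0.9/n), is 7.5, 6.7 or 5.9 points in Test and 8.7 in Reference, so the distance is 0.5 to 0.6 SE. At d = 20 the distances double, to a little over 1 SE.

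**What small cells can show.** With zero events in n, the upper end of a two-sided 95% interval is 1 − 0.025^(1/n): 13.2% at n = 26, 16.8% at n = 20, 26.5% at n = 12 and 45.9% at n = 6. The one-sided 95% limit at n = 6 is 1 − 0.05^(1/6) = 39.3%.

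**The case against.** The main objection is that the SAP normally settles table columns, and it cannot be seen. Summarising by treatment group does not rule out a split by study part, and the protocol already handles Part B pharmacokinetics separately. This stands: the point concerns only what the protocol states.

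It can also be said that no objective is missed. Secondary objective (b) in Section 3 is the safety and tolerability of each treatment, and there is no separate paediatric safety objective. A by-arm table meets that wording, so a reader who infers that the plan fails its own objective goes too far.

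Third, much of the information is kept. Section 11.5.3 says: "All information pertaining to AEs noted during the study will be listed by subject". Section 7.6 says of local reactions: "An AE should be recorded if the severity is worse than at Day 1". Age is collected under Section 7.3. With about 62 subjects, paediatric AE counts could be put together by hand, so it would be wrong to infer that paediatric safety data are lost. What remains is narrower: age is not among the fields named for that listing, no listing of the tolerance scores is stated, and a listing is not a table with denominators.

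Finally, the size of the effect rests on assumed age differences. That is correct, and it is why no material bias is claimed.

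**Conclusion.** The point holds as a minor, cheap improvement. As stated in the protocol, the TEAE and tolerance tables give no paediatric rate and pool over the factor used to stratify randomisation. The age mix in the arm contrast is about 7% to 18% of any adult-child difference, depending on whether 16, 20 or 26 children receive Test, and at most about a third of a standard error in the cases worked.

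A reader might infer that pooling materially distorts the Test-Reference comparison, or that the trial plans no paediatric safety summary at all. The documents support neither. They give no age-specific rate, the effect is within noise for moderate differences, and the SAP may already contain the split. The assumptions are the illustrative rates and, for the 16 and 20 cases, a Reference paediatric group that stays at 12.

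**What to change.** In Sections 11.5.2 and 11.5.3, and in the SAP, present the TEAE and tolerance tables descriptively by treatment within the two randomisation strata: adult (17 or older) and paediatric. Keep the pooled column as a total. Show Test ages 9-11 as counts only. Ages 12-16 can then be compared like for like, because Reference enrols nobody under 12. If the SAP already does this, nothing needs to change.

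The cost is table programming and a few sentences; no new data, sample size or error rate is involved. The downside is more columns with small denominators: 12 per arm in adults, about 26 or fewer Test children against 12 Reference, and about 6 at ages 9-11, where a percentage would say very little.

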11.5.4 Vital Signs

Changes from Baseline in vital signs (blood pressure and pulse) will be summarized by treatment group at each evaluation visit using descriptive statistics.

11.5.5 Electrocardiogram

A 12-lead Electrocardiogram (ECG) will be performed and must be without clinically significant abnormality.

11.5.6 Physical Examination

The physical examination will include measurement of vital signs (blood pressure, pulse rate and body temperature) and a review of the following: Head, Eyes, Ears, Nose, Throat (HEENT), neck, chest, back, abdomen, extremities, skin (face, neck, shoulders, upper chest and upper back) and neurological function.

Demographic data (age, gender, race, body weight adjusted for indoor clothing, height, BMI), and alcohol and smoking habits will be recorded.

11.5.7 Safety Laboratory Values

General Biochemistry: Sodium, potassium, chloride, glucose, blood urea nitrogen (BUN), creatinine, bilirubin total, alkaline phosphatase, AST, ALT and albumin

Hematology: White cell count with differential (absolute values of neutrophil, lymphocyte, monocyte, eosinophil, and basophil), red cell count, hemoglobin, hematocrit, mean corpuscular volume (MCV), and platelets count

Urinalysis: Color, clarity, specific gravity, pH, leukocyte, protein, glucose, ketones, bilirubin, blood, nitrite, urobilinogen. Microscopic examination will only be performed if the dipstick test is outside of the reference range for leukocyte, blood, nitrite or protein

Additional laboratory tests may be also performed by the medical laboratory as part of larger standard tests panels although not required for the subject's safety. All test results will be

assessed by physician for clinical significance. Only test results required by the protocol will be entered in the clinical database and reported in the Clinical Study Report.

Results of urine pregnancy tests will be provided in a data listing.

APPENDIX 1: DECLARATION OF HELSINKI (2013)

Adopted by the 18th WMA General Assembly, Helsinki, Finland, June 1964, and amended by the:
29th WMA General Assembly, Tokyo, Japan, October 1975
35th WMA General Assembly, Venice, Italy, October 1983
41st WMA General Assembly, Hong Kong, September 1989
48th WMA General Assembly, Somerset West, Republic of South Africa, October 1996
52nd WMA General Assembly, Edinburgh, Scotland, October 2000
53rd WMA General Assembly, Washington 2002 (Note of Clarification on paragraph 29 added)
55th WMA General Assembly, Tokyo 2004 (Note of Clarification on Paragraph 30 added)
59th WMA General Assembly, Seoul, October 2008
64th WMA General Assembly, Fortaleza, Brazil, October 2013

A. PREAMBLE

1. The World Medical Association (WMA) has developed the Declaration of Helsinki as a statement of ethical principles for medical research involving human subjects, including research on identifiable human material and data.
The Declaration is intended to be read as a whole and each of its constituent paragraphs should be applied with consideration of all other relevant paragraphs.
2. Consistent with the mandate of the WMA, the Declaration is addressed primarily to physicians. The WMA encourages others who are involved in medical research involving human subjects to adopt these principles.

B. GENERAL PRINCIPLES

3. The Declaration of Geneva of the WMA binds the physician with the words, “The health of my patient will be my first consideration,” and the international Code of Medical Ethics declares that “A physician shall act in the patient’s best interest when providing medical care.”
4. It is the duty of the physician to promote and safeguard the health, well-being and rights of patients, including those who are involved in medical research. The physician's knowledge and conscience are dedicated to the fulfillment of this duty.
5. Medical progress is based on research that ultimately must include studies involving human subjects.
6. The primary purpose of medical research involving human subjects is to understand the causes, development and effects of diseases and improve preventive, diagnostic and therapeutic interventions (methods, procedures and treatments). Even the best current interventions must be evaluated continually through research for their safety, effectiveness, efficiency, accessibility and quality.
7. Medical research is subject to ethical standards that promote and ensure respect for all human subjects and protect their health and rights.
8. While the primary purpose of medical research is to generate new knowledge, this goal can never take precedence over the rights and interests of individual research subjects.
9. It is the duty of physicians who are involved in medical research to protect the life, health, dignity, integrity, right to self-determination, privacy, and confidentiality of personal information of research subjects. The responsibility for the protection of research subjects must always rest with the physician or other health care professionals and never with the research subjects, even though they have given consent.
10. Physicians must consider the ethical, legal and regulatory norms and standards for research involving human subjects in their own countries as well as applicable international norms and standards. No national or international ethical, legal or regulatory requirement should reduce or eliminate any of the protections for research subjects set forth in this Declaration.
11. Medical research should be conducted in a manner that minimizes possible harm to the environment.

12. Medical research involving human subjects must be conducted only by individuals with the appropriate ethics and scientific education, training and qualifications. Research on patients or healthy volunteers requires the supervision of a competent and appropriately qualified physician or other health care professional.
13. Groups that are underrepresented in medical research should be provided appropriate access to participation in research.
14. Physicians who combine medical research with medical care should involve their patients in research only to the extent that this is justified by its potential preventive, diagnostic or therapeutic value and if the physician has good reason to believe that participation in the research study will not adversely affect the health of the patients who serve as research subjects.
15. Appropriate compensation and treatment for subjects who are harmed as a result of participating in research must be ensured.

C. RISK, BURDENS AND BENEFITS

16. In medical practice and in medical research, most interventions involve risks and burdens.
Medical research involving human subjects may only be conducted if the importance of the objective outweighs the risks and burdens to the research subjects.
17. All medical research involving human subjects must be preceded by careful assessment of predictable risks and burdens to the individuals and groups involved in the research in comparison with foreseeable benefits to them and to other individuals or groups affected by the condition under investigation.
Measures to minimize the risks must be implemented. The risks must be continuously monitored, assessed and documented by the researcher.
18. Physicians may not be involved in a research study involving human subjects unless they are confident that the risks have been adequately assessed and can be satisfactorily managed.
When the risks are found to outweigh the potential benefits or when there is conclusive proof of definitive outcomes, physicians must assess whether to continue, modify or immediately stop the study.

D. VULNERABLE GROUPS AND INDIVIDUALS

19. Some groups and individuals are particularly vulnerable and may have an increased likelihood of being wronged or of incurring additional harm.
All vulnerable groups and individuals should receive specifically considered protection.
20. Medical Research with a vulnerable group is only justified if the research is responsive to the health needs or priorities of this group and the research cannot be carried out in a non-vulnerable group. In addition, this group should stand to benefit from the knowledge, practices or interventions that result from the research.

E. SCIENTIFIC REQUIREMENTS AND RESEARCH PROTOCOLS

21. Medical research involving human subjects must conform to generally accepted scientific principles, be based on a thorough knowledge of the scientific literature, other relevant sources of information, and adequate laboratory and, as appropriate, animal experimentation. The welfare of animals used for research must be respected.
22. The design and performance of each research study involving human subjects must be clearly described and justified in a research protocol. The protocol should contain a statement of the ethical considerations involved and should indicate how the principles in this Declaration have been addressed. The protocol should include information regarding funding, sponsors, institutional affiliations, potential conflicts of interest, incentives for subjects and information regarding provisions for treating and/or compensating subjects who are harmed as a consequence of participation in the

research study. In clinical trials, the protocol must also describe appropriate arrangements for post-trial provisions.

F. RESEARCH ETHICS COMMITTEES

23. The research protocol must be submitted for consideration, comment, guidance and approval to the concerned research ethics committee before the study begins. This committee must be transparent in its functioning, must be independent of the researcher, the sponsor and any other undue influence and must be duly qualified. It must take into consideration the laws and regulations of the country or countries in which the research is to be performed as well as applicable international norms and standards but these must not be allowed to reduce or eliminate any of the protections for research subjects set forth in this Declaration. The committee must have the right to monitor ongoing studies. The researcher must provide monitoring information to the committee, especially information about any serious adverse events. No amendment to the protocol may be made without consideration and approval by the committee. After the end of the study, the researchers must submit a final report to the committee containing a summary of the study's findings and conclusions.

G. PRIVACY AND CONFIDENTIALITY

24. Every precaution must be taken to protect the privacy of research subjects and the confidentiality of their personal information.

H. INFORMED CONSENT

25. Participation by individuals capable of giving informed consent as subjects in medical research must be voluntary. Although it may be appropriate to consult family members or community leaders, no individual capable of giving informed consent may be enrolled in a research study unless he or she freely agrees.
26. In medical research involving human subjects capable of giving informed consent, each potential subject must be adequately informed of the aims, methods, sources of funding, any possible conflicts of interest, institutional affiliations of the researcher, the anticipated benefits and potential risks of the study and the discomfort it may entail, post-study provisions and any other relevant aspects of the study. The potential subject must be informed of the right to refuse to participate in the study or to withdraw consent to participate at any time without reprisal. Special attention should be given to the specific information needs of individual potential subjects as well as to the methods used to deliver the information. After ensuring that the potential subject has understood the information, the physician or another appropriately qualified individual must then seek the potential subject's freely-given informed consent, preferably in writing. If the consent cannot be expressed in writing, the non-written consent must be formally documented and witnessed. All medical research subjects should be given the option of being informed about the general outcome and results of the study.
27. When seeking informed consent for participation in a research study the physician should be particularly cautious if the potential subject is in a dependent relationship with the physician or may consent under duress. In such situations the informed consent should be sought by an appropriately qualified individual who is completely independent of this relationship.
28. For a potential research subject who is incapable of giving informed consent, the physician must seek informed consent from the legally authorized representative. These individuals must not be included in a research study that has no likelihood of benefit for them unless it is intended to promote the health of the group represented by the potential subject, the research cannot instead be performed with persons capable of providing informed consent, and the research entails only minimal risk and minimal burden.
29. When a potential research subject who is deemed incapable of giving informed consent is able to give assent to decisions about participation in research, the physician must seek that assent in addition to the consent of the legally authorized representative. The potential subject's dissent should be respected.

30. Research involving subjects who are physically or mentally incapable of giving consent, for example, unconscious patients, may be done only if the physical or mental condition that prevents giving informed consent is a necessary characteristic of the research group. In such circumstances the physician must seek informed consent from the legally authorized representative. If no such representative is available and if the research cannot be delayed, the study may proceed without informed consent provided that the specific reasons for involving subjects with a condition that renders them unable to give informed consent have been stated in the research protocol and the study has been approved by a research ethics committee. Consent to remain in the research should be obtained as soon as possible from the subject or a legally authorized representative.
31. The physician must fully inform the patient which aspects of their care are related to the research. The refusal of a patient to participate in a study or the patient's decision to withdraw from the study must never adversely affect the patient-physician relationship.
32. For medical research using identifiable human material or data, such as research on material or data contained in biobanks or similar repositories, physicians must seek informed consent for its collection, storage and/or reuse. There may be exceptional situations where consent would be impossible or impracticable to obtain for such research. In such situations the research may be done only after consideration and approval of a research ethics committee.

I. USE OF PLACEBO

33. The benefits, risks, burdens and effectiveness of a new intervention must be tested against those of the best proven intervention(s), except in the following circumstances:
 - a. Where no proven intervention exists, the use of placebo, or no intervention, is acceptable; or
 - b. Where for compelling and scientifically sound methodological reasons the use of any intervention less effective than the best proven one, the use of placebo, or no intervention is necessary to determine the efficacy or safety of an intervention and the patients who receive any intervention less effective than the best proven one, placebo, or no intervention will not be subject to additional risks of serious or irreversible harm as a result of not receiving the best proven intervention. Extreme care must be taken to avoid abuse of this option.

J. POST-TRIAL PROVISIONS

34. In advance of a clinical trial, sponsors, researchers and host country governments should make provisions for post-trial access for all participants who still need an intervention identified as beneficial in the trial. This information must also be disclosed to participants during the informed consent process.

K. RESEARCH REGISTRATION AND PUBLICATION AND DISSEMINATION OF RESULTS

35. Every research study involving human subjects must be registered in a publicly accessible database before recruitment of the first subject.
36. Researchers, authors, sponsors, editors and publishers all have ethical obligations with regard to the publication and dissemination of the results of research. Researchers have a duty to make publicly available the results of their research on human subjects and are accountable for the completeness and accuracy of their reports. All parties should adhere to accepted guidelines for ethical reporting. Negative and inconclusive as well as positive results must be published or otherwise made publicly available. Sources of funding, institutional affiliations and conflicts of interest should be declared in the publication. Reports of research not in accordance with the principles of this Declaration should not be accepted for publication.
37. In the treatment of an individual patient, where proven interventions do not exist or other known interventions have been ineffective, the physician, after seeking expert advice, with informed consent from the patient or a legally authorized representative, may use an unproven intervention if in the physician's judgment it offers hope of saving life, re-establishing health or alleviating suffering. This intervention should subsequently be made the object of research, designed to evaluate its safety and efficacy. In all cases, new information must be recorded and, where appropriate, made publicly available. October 2013
